5.3 Adverse Events and Serious Adverse Events

This group of trial participants are expected to have a lot of complications. It is the established practice in trials on critically ill patients that adverse events are part of the natural trajectory of the primary disease process or expected complications of the critical illness.²⁷

Therefore, we have chosen to record only the following AEs:

- Atelectasis
- Irritability of airway mucosa

We will register all SAEs. The registration will be done in REDCap and once a SAE registration is complete, the sponsor and coordinating investigator will receive an e-mail notification within 24 hours via the REDCap notification e-mail system. Thus, the law on immediate notifying (within 24 hours after it has come to an investigator's knowledge) the sponsor about SAEs is being followed.

5.4 Suspected Unexpected Serious Adverse Reactions

All potential SUSARs will be reported to the sponsor within 24 hours of discovery. If the sponsor believes that a trial participant has a SUSAR which results in death or is in a life-threatening condition, it will be reported as soon as possible to the Danish Medicines Agency and The Committee on Health Research Ethics and no later than 7 days after it has come to sponsor's knowledge. No later than 8 days after the report (15 days in total), sponsor must inform the mentioned authorities about all relevant information on the follow-up of the SUSAR. All other trial participants that have a SUSAR that do not result in death or in life-threatening conditions must be reported no later than 15 days after sponsor has been made aware of these.

5.5 Reporting

Once a year, a report with all SUSARs will be sent to The Danish Medicines Agency and The Committee on Health Research Ethics.

After the last trial participant, last visit (1420 trial participants with a complete 30-day, 6- and 12-month follow-up), the end of the trial will be reported within 90 days to the relevant authorities or according to national law. All events, reactions and results of the study will be reported to the EudraCT database results within a year after termination of the study.

6. Study administration

6.1 Ethics and dissemination

Trial participant insurances will be in place at all trial centres either through the national health insurance or through specifically supplied local trial insurances as required according to the specific trial centres and national regulations.

This RCT will be conducted in compliance with the published trial protocol, the Helsinki Declaration in its latest version,²⁸ the Good Clinical Practice (GCP) guidelines²⁹ and national laws in the participating countries. The protocol will be sent to the Danish Committee on Health Research Ethics for the Capital Region of Denmark and The Danish Medicines Agency. It will be monitored by the regional Good Clinical Practice Unit. Data management must be approved according to national legislation. We have written the protocol in accordance with the SPIRIT 2013 Statement¹⁹ and will register the trial in the www.clinicaltrials.gov and European Union Drug Regulating Authorities Clinical Trials (EudraCT) registries before the enrolment of the first trial participant. No substantial deviation from the protocol will be implemented without prior review and approval of the regulatory authorities except where it may be necessary to eliminate an immediate hazard to the trial participants. In such case, the deviation will be reported to the authorities as soon as possible.

As stated in section 3.4.2 regarding consent procedures in Denmark, the trial participants in this study are considered temporarily incompetent because of the acute and severe condition related to their traumatic injuries. Symptoms will include severe pain, impaired consciousness, and early complications are circulatory and respiratory failure requiring emergency intubation. Some of these trial participants are expected to die. Current practice is that supplemental oxygen is administered as soon as possible after trauma often prehospitally. Thus, the intervention tested in this trial is pivotal to be given immediately in the early phase after trauma. Furthermore, it is stated above that a liberal supplemental oxygen strategy may be detrimental and should be avoided as soon as possible. Therefore, we cannot delay enrolment and need to use the consent procedures for emergency research. To make clinical trials with the goal of improving the treatment of traumatic injuries it is necessary to include unconscious and incompetent patients as no clinically relevant animal model exists. In other countries, national law will be followed in terms of including patients considered temporarily incompetent.

Oxygen is a well-known drug given in a dosage of FiO_2 0.21-1.0 and can be administered by paramedics, nurses, and doctors. The side-effects of normobaric oxygen-strategies include slightly decreased heart rate as well as increased risk of atelectasis, pleuritis and respiratory distress syndrome. The greater the FiO_2 , the greater the risk. As the standard treatment of care currently includes high levels of FiO_2 , it seems plausible that the intervention group will have a decreased risk for developing these side-effects. On the other side, hypoxia is documented to be deleterious. To avoid the risk of hypoxia, all trial participants will be monitored with continuous pulse oximetry and arterial blood gases to avoid desaturation. If the saturation is unmeasurable due to e.g. hypovolemia or hypothermia the treating physician will decide and document the treatment of choice. When measurable again, the allocated intervention will resume. In the TRAUMOX1 trial, we observed only seven episodes of desaturation (SpO_2 below 90%) in the restrictive group (median 87% [87-89]). Of note, five of the seven cases of SpO_2 below 89% occurred in two trial participants; one trial participant who had just been extubated and another trial participant who went into cardiac arrest for another reason than hypoxemia.

The trial participants receiving the standard treatment and what is recommended in current guidelines (liberal oxygen) will not be put at any additional risk compared to trial participants not enrolled in the study. However, we suspect this standard treatment is not always beneficial. As outlined in the background section, we hypothesise that a liberal supplemental oxygen strategy may be detrimental and should be avoided as soon as possible. Thus, the restrictive supplemental oxygen (intervention group) may be associated with fewer side effects, with no additional risk, as seen in other trial participant populations. Therefore, we believe that this study may be beneficial for the single trial participant. Finally, there will be no risk of delaying treatment due to enrolment, as the treating physician will be treating the trial participant as usual, until the randomisation results are available, and the allocation has begun. Therefore, we think that the study will add no risk for the included trial participants.

6.2 Timeline of study progress

Approvals will be applied for spring 2021 initially in Denmark. First inclusion is expected autumn 2021, enrolment completed spring 2023 and data analysis and manuscript drafting autumn 2023. The submission of primary paper is expected at the beginning of year 2024. See figure 2.

6.3 Publication publicity

The study results will be published in an appropriate international peer-reviewed scientific journals. When study results are published, it will be announced on the study website <https://www.traumox2.org/>. The study will be registered, and study results will be disclosed by the coordinating principal investigator in one or more public clinical study registry(ies), according to national/international use, including both positive, negative and inconclusive results. The registration will include a list of the investigational centres. The steering committee and the primary centre investigator (active) will be listed as co-authors in the publications. If the centre involves prehospital inclusion the prehospital centre investigator (active) will be co-author. Top-enrolling centres will be able to designate one additional co-author for every completely documented 100 trial participants. All authors must fulfil the criteria for authorship according to the ICMJE group. Each contributing centre can designate a reasonable number of active collaborators that participates in the study administration. These collaborators will be mentioned in the TRAUMOX2-study group and will be trackable via PubMed. In line with the principles of data preservation and sharing, the steering committee will, after publication of the overall dataset, consider all reasonable requests to make the dataset available in whole or part for secondary analyses and scientific publication. The steering committee will consider proposals for secondary analyses on the basis of the scientific quality of the proposal. Proposals will need to be revised and approved by the steering committee prior to submission.

6.4 Data monitoring and safety committee (DMSC)

An independent data monitoring- and safety committee (DMSC) will be set up. The committee will include a statistician. The committee will meet when 30-day follow-up of 355 (approximately 25% of the sample size estimation) and 710 (approximately 50% of the sample size estimation) trial participants has been obtained. Prior to the meeting, a biostatistician will perform an interim analysis with blinded data provided by the sponsor and principal investigator. Criteria for premature termination will be decided by steering committee. Furthermore, the sponsor has the responsibility to report the overall number of serious adverse events (SAEs) yearly to the DMSC. The DMSC charter has been approved by DMSC members and the Danish Medicines Agency. The content of the charter is:

Charter for the Data Monitoring and Safety Committee (DMSC) for TRAUMOX2

Version 1.0

Date: 21-12-2021

Comparing Restrictive versus Liberal Oxygen Strategies for Trauma
Patients: The TRAUMOX2 Trial

EudraCT number: 2021-000556-19

Danish Research Ethics Committee number: H-21018062

ClinicalTrials.gov number: NCT05146700

Chief investigator and sponsor: [name], M.D., Ph.D.

Introduction

This charter will define the responsibilities of the independent DMSC, the members, the purpose of the DMSC and the timing of the meetings. The DMSC is answerable for the safety of trial participants, assessing the safety and efficacy of the interventions during the trial, and for monitoring the overall conduct of the clinical trial. The DMSC is obliged to follow the EU Clinical Trials Directive 2001/20/EC while assessing the study and to keep all patient-level data confidential. The DMSC consists of three clinicians with expertise in critical emergency care research and an independent biostatistician. The DMSC members have been chosen in order to avoid any financial or intellectual conflicts of interest. The members have agreed to this task for the entire duration of the clinical trial. However, should any members leave the DMSC during the trial, the steering committee will appoint the replacement(s). The DMSC is independent from the sponsor and the trial investigators. The DMSC will be notified of all changes to the protocol or changes in trial conduct. The clinicians of the DMSC will be unpaid. The biostatistician will be paid for the hours spent on data analysis prior to the DMSC meetings.

Timing of the meetings

Two interim analysis meetings will be held to review data relating to treatment efficacy, patient safety, and quality of trial conduct (e.g. enrollment progression). The four members of the DMSC will meet either physically or online when 30-day follow-up data (primary outcome) of 355 (approximately 25 % of sample size estimation) and 710 (approximately 50 % of sample size estimation) patients have been obtained. The trial will continue while the DMSC review the data. The DMSC will be specifically notified by e-mail by the sponsor or coordinating investigator when approximately 20 % and 45 % of the patients are included due to scheduling and arranging the first and second meeting. Furthermore, it is optional for the DMSC members to receive the newsletters from the trial. The DMSC will be responsible for scheduling and arranging the meetings. Data will be provided to the DMSC at least 5 days prior to their meetings.

Interim data review

The DMSC will review non-identifiable person data for 30-day mortality at the two predetermined time points. In addition, at the second interim analysis, the DMSC will also consider available data on major lung complications defined as pneumonia and acute respiratory distress syndrome within 30 days after trauma. The DMSC can at any time request extra reviews if necessary. The data will be provided to the biostatistician in Excel. One row will represent one trial participant and each column will be a data variable. The data variables included in the raw data output are:

1: record_id (a number that uniquely identifies the patient)

2: scr_incl_randomisation (the randomisation code: group A or B)

3: outc_prim_spec___1 (occurrence of death within 30 days: 0 = no, 1 = yes)

4: outc_prim_spec___2 (occurrence of pneumonia within 30 days: 0 = no, 1 = yes)

5: outc_prim_spec___3 (occurrence of acute respiratory distress syndrome within 30 days: 0 = no, 1 = yes)

The DMSC statistician will provide aggregate data analysis for variable 3, 4 and 5 in two-by-two tables stratified on variable 2 (renamed randomisation code blinded by an external person). The data provided is only to evaluate on treatment efficacy and patient safety. Thus, no other data variables will be provided.

The DMSC may recommend stopping the trial at each of the two interim analyses if a major difference in 30-day mortality is found. There are no strict stopping criteria, but it is suggested that the recommendation should be based on only a considerable difference, such as a relative risk where the lower limit of the 95 % CI is >2 (regardless of which group is nominator). The same applies to both the first and second interim analysis. There should be no premature ending of the trial for futility before completion of the preplanned inclusion of 1420 patients with a complete 30-day follow-up.

Content of the DMSC reports

After each of the two reviews, the DMSC will produce a short report to the steering committee with recommendations for continuation, modifications, or premature termination of the trial. The DMSC will be advisory to the steering committee. Therefore, the final decision regarding potential modifications or termination will rest with the steering committee.

Members of the DMSC

[name] [name], Ph.D.

Chairman of the Data Monitoring and Safety Committee

Professor

Department of Anesthesia and Intensive Care

Aalborg University Hospital

[name] [name], M.P.H., Ph.D., D.M.Sc.

Member of the Data Monitoring and Safety Committee

Associate professor

Department of Anesthesiology and Intensive Care Medicine

Aarhus University Hospital
Research Center for Emergency Medicine
Aarhus University Hospital and Aarhus University
Prehospital Emergency Medical Services
Central Denmark Region

[name], Ph.D.

Member of the Data Monitoring and Safety Committee
Associate professor
Consultant Anaesthesiologist and pre-hospital critical care doctor
Department of Research and Development
Norwegian Air Ambulance Foundation
Oslo, Norway Air Ambulance Department
Division of Prehospital Services
Oslo University Hospital
Norway Faculty of Health Sciences, University of Stavanger
Stavanger, Norway

[name], biostatistician

Member of the Data Monitoring and Safety Committee
Assistant professor
Department of Public Health, Section of Biostatistics
University of Copenhagen
Denmark
Neurobiology Research Unit and BrainDrugs
Copenhagen University Hospital
Rigshospitalet
Denmark

Read and agreed by

[name]

Date: 20-12-2021

Signature: 

[name]

Date: **[name]**
Signature: **[name]**  Digitally signed by [name]
Date: 2021.12.14 18:20:58 +01'00'

[name]

Date: **13.12.2021**

Signature: 

[name]

Date: 19-12-2021

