3.4.1 Randomisation and blinding

Trial participants will be randomised 1:1 in variable block sizes and stratified by centre (pre-hospital base or trauma centre) and tracheal intubation at inclusion. The randomisation table will be generated outside of our electronic database REDCap (explained in section 3.7.2) by a biostatistician otherwise not connected to the study. The allocation sequence list and block sizes will only be known by the statistician and will remain

concealed from the investigators. Randomisation will be determined after proxy consent (or according to local legislation in each country) from opening a concealed envelope with information on allocation. The envelopes will be located both pre-hospital and in-hospital. Each concealed envelope will contain a study ID that matches a study ID in the randomisation list generated by the statistician.

The study will be an international, multicentre, parallel-grouped, superiority, outcome assessor- and analyst-blinded, randomised, controlled, clinical trial with regards to treatment: treating staff will be aware of the trial participants' randomisation group. While including trial participants for the study, the research team will be aware of the trial participants' oxygen allocation strategy. However, at least two allocation blinded primary outcome assessors (specialists in anaesthesia, intensive care, emergency medicine or similar) will be appointed at each centre to assess in-hospital lung complications (pneumonia and ARDS). Blinding will be ensured by concealing all information indicative of the allocation prior to assessment. The statistician and manuscript writers will be blinded towards the allocation of treatment once the trial ends when data is being analysed and the manuscript is drafted.

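### The DMSC's planned interim file does not let it compare SAEs or hypoxaemia between groups; separately, the charter's one numerical example for recommending a stop is a high bar whose operating characteristics are not stated

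*Protocol*

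**What the plan says.** All of this is in Protocol 6.4 and the charter reproduced there.

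**Remit.** The charter's introduction makes the committee responsible for "assessing the safety and efficacy of the interventions during the trial, and for monitoring the overall conduct of the clinical trial".

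**Data.** Under *Interim data review*, the file for the DMSC statistician has five columns: record identifier, group code (A or B), and yes/no indicators for death, pneumonia and ARDS within 30 days. The charter adds: "The data provided is only to evaluate on treatment efficacy and patient safety. Thus, no other data variables will be provided". Mortality is scheduled for review at both looks and lung complications only at the second. Outside the file, "the sponsor has the responsibility to report the overall number of serious adverse events (SAEs) yearly to the DMSC". The DMSC may ask for extra reviews at any time, but the charter does not say what these may contain.

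**Guide for stopping.** The charter says: "There are no strict stopping criteria, but it is suggested that the recommendation should be based on only a considerable difference, such as" a 30-day mortality "relative risk where the lower limit of the 95 % CI is >2 (regardless of which group is nominator". It continues: "The same applies to both the first and second interim analysis". The looks come when 30-day data on "355 (approximately 25 % of sample size estimation) and 710 (approximately 50 % of sample size estimation) patients have been obtained". The DMSC advises and the steering committee decides.

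**Hypoxaemia.** Protocol 3.6.2 lists episodes of saturation below 90% during the intervention as a secondary outcome. Section 6.1 acknowledges that hypoxia does harm and reports seven desaturation episodes in the pilot's restrictive group.

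**The concern.** These are two separate weaknesses.

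**What the committee can see.** The synopsis (risk-benefit assessment) and section 6.1 rely on continuous oximetry and blood gases to keep the restrictive arm from desaturating. Whether that works is a between-group question that accumulating data can answer. The planned file omits the variable needed, and an overall SAE count cannot show an imbalance. At the first look, mortality is the only outcome scheduled for review. A committee charged with participants' safety, in a trial that enrols people unable to consent, would then have to judge that safety mainly from deaths.

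**How the one number reads.** The charter gives a single numerical anchor, says a recommendation should rest only on a considerable difference, and does not say how often its example would be met. An example that demands a lower confidence limit above 2 needs an observed relative risk near 3. A difference in deaths that most statisticians would call convincing can therefore lie below the suggested level.

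**Working it through.** **Data content: passages side by side.**

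| Item | Collected in the trial? | Planned for the DMSC by group? |
|---|---|---|
| Death, 30 days | Yes | Yes, both looks |
| Pneumonia, ARDS | Yes | In the file; considered at look 2 |
| SpO2 <90% during intervention | Yes (3.6.2) | No |
| SAEs | Yes (5.3) | No; yearly overall number |

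"Overall number" is not explicitly defined as pooled over groups, but that is its natural reading, and the file that carries the group code has no SAE column.

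**Guide: inputs.**
- Looks at 355 and 710 patients (charter). Against the target of 1420, 355/1420 = 25% and 710/1420 = 50%, as stated.
- "Trial participants will be randomised 1:1 in variable block sizes" (3.4.1), so about 178 and 177 per arm at look 1, and 355 per arm at look 2.
- Mortality in the lower-risk arm: 6-12%, the literature range for trauma in 3.8, with 9% as its middle. Applying it to this arm is an assumption.
- True relative risks of 2, 2.5 and 3 are illustrative; the documents state none.

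The plan gives no operating characteristics for the guide, so there is no stated figure to reproduce.

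**Formula.** With deaths d1 and d0 among n1 and n0 patients, RR = (d1/n1)/(d0/n0), SE(ln RR) = √(1/d1 − 1/n1 + 1/d0 − 1/n0), and the lower limit is RR × exp(−1.96 × SE).

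**Worked example at look 2: 64 vs 32 deaths, 355 per arm.**
- RR = 64/32 = 2.0.
- SE = √(1/64 + 1/32 − 2/355) = √(0.01563 + 0.03125 − 0.00563) = 0.203.
- 95% CI = 2.0 × exp(±1.96 × 0.203) = 1.34 to 2.98.
- Pooled two-proportion test: pooled risk 96/710 = 0.1352; z = (32/355)/√(0.1352 × 0.8648 × 2/355) = 0.0901/0.0257 = 3.51; P = 0.0004.
- The lower limit of 1.34 is well below 2.

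**Counts that just reach the level at about 9%.** Look 2: 94 vs 32 deaths (26% vs 9%; RR 2.94, lower limit 2.02), while 93 vs 32 just fails. Look 1: 54 vs 16 deaths (31% vs 9%; lower limit 2.02), while 53 vs 16 fails. Over 6-12% mortality, with the lower-risk arm at its expected count, the observed RR must be about 3.2-3.8 at look 1 and 2.8-3.2 at look 2.

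**Chance of reaching the level (look 1 / look 2).** This is the exact sum over two independent binomials of all outcomes whose lower limit exceeds 2.

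| True RR | 6% | 9% | 12% |
|---|---|---|---|
| 2 | 1.6% / 2.0% | 1.8% / 2.1% | 1.9% / 2.1% |
| 2.5 | 6.8% / 12.8% | 10% / 19% | 13.7% / 25.8% |
| 3 | 19% / 39% | 30% / 58% | 43% / 74% |

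The first row is near 2.5% by construction: when the true RR equals the limit, a 95% lower bound exceeds it about 2.5% of the time in large samples. The other rows tell the reader more.

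**Comparison guide.** Two-sided P<0.001 from the pooled test, at 9% mortality: 20% / 59% under RR 2 (30-82% at look 2 over 6-12%) and 59% / 96% under RR 2.5. With no true difference, the chance is at most 0.1% per look.

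**The case against.** **The guide is not a boundary.** The charter disclaims strict criteria, introduces the figure as an example, and leaves the DMSC free to recommend modification or stopping for a major difference in mortality. This stands. A reader might infer that a doubling of deaths would go unacted on 98% of the time. The documents do not support that: the 2% is the chance of reaching a suggested level, and says nothing about what the members would recommend.

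**The 2% is built in.** Also correct, which is why the results for RR 2.5 and 3 are shown. They still describe a demanding guide.

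**The missing safety data do not cause the 2%.** A reader might link the two; they are unrelated. The 2% comes from the threshold alone.

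**The data are not closed off.** Extra reviews may be requested, SAEs go to the sponsor within 24 hours (5.3), SUSARs are reported (5.4), and participants are monitored continuously (6.1). These routes matter, but none is a planned comparison between groups, and the content of an extra review is not specified.

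**A high, symmetric bar can be deliberate.** The DMSC members and the Danish Medicines Agency approved the charter. That is fair: P<0.001 is another convention, and moving from about 2% to 59% at look 2 under RR 2 is a real change. Applied symmetrically, it would also make early stopping for apparent benefit easier.

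**Timing.** The sub-study SAP (sections 2.3 and 6) implies that TRAUMOX2 inclusion was to end in September 2023, so both looks may already have passed. The documents do not report when they were held.

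**Conclusion.** The data point stands on the text. The planned reviews do not let the DMSC compare SAEs or hypoxaemia between groups, although both are recorded and hypoxaemia is the recognised hazard of the restrictive arm. It is right to say that the planned file omits these data. It would go too far to say that the committee is barred from ever obtaining them.

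The guide point is weaker and a matter of judgement. The only numerical example is reached about 2% / 2% of the time under a true RR of 2, 10% / 19% under 2.5 and 30% / 58% under 3, at 355 and 710 patients. A split of 64 vs 32 deaths with P = 0.0004 would fall below it. This rests on 9% mortality in the lower-risk arm, equal arms and a Wald interval. Varying mortality over 6-12% hardly moves the RR 2 figures but changes those for 2.5 and 3 considerably. The charter should state these properties so that the members know what the example implies; the present choice is not an error.

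**What to change.** **Data (the main change).** Add to the existing export, by masked group at both looks: participants with any SpO2 <90% during the intervention, and participants with any SAE. Since deaths are already supplied and count as SAEs, a column for any non-fatal SAE would tell the committee more. Amend the sentence that excludes other variables, and say what an extra review may contain. Cost: two or three columns of data already recorded, and a charter amendment. Downside: hypoxaemia counts may let the DMSC infer which masked group is which. An any-SAE column may also discriminate poorly in patients with many expected complications.

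**Guide (for consideration).** State the operating characteristics of the present example. The steering committee and DMSC could then consider a less extreme advisory guide for harm, such as two-sided P<0.001 for 30-day mortality at each look. They should decide explicitly whether it also applies to apparent benefit, because a symmetric guide would ease early stopping in that direction too. The false-alarm cost is at most 0.1% per look.

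If both looks have already been held, neither change can act on them; the report should then state what the DMSC saw and which guide it had.
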